3.4.3 Expected duration of participant participation

Study participants will be participating in the study until a clinical decision on diagnosis has been made. This is expected to be a maximum of 6 months (and frequently a shorter period of time).

Page 22 of 53

IDEAL BACKPACS Protocol Final Version 1.1 date 09-Oct-l2024

3.4.4 Removal of participants from therapy or assessments/Participant Withdrawal

Participants may be withdrawn from the study either at their own request or at the discretion of the Investigator. The participants will be made aware that this will not affect their future care. Participants will be made aware (via the information sheet and consent form) that should they withdraw the data collected to date cannot be erased and may still be used in the final analysis.

Participants may withdraw their consent for follow-up and other study-related activities including receiving study related communications. The NCTU must be informed of all requests by participants to stop their involvement in the study; appropriate action will be taken to ensure that the participant's wishes are followed.

Sites will be trained to determine which activities participants may wish to withdraw from.

Withdrawal type	Withdrawal procedure	Use of data
Discontinue from study communications	Any participant who requests to be withdrawn from other study communications will be removed from all mailing lists for ongoing study contact (e.g. newsletters and reminders).	N/A withdrawal from communications only.
Collection of data from medical records and/or NHS Digital	Any participant that requests to discontinue collection of routine data will be directed to the national data opt out service.	Any data collected prior to participant withdrawal will be retained and used.
Full study withdrawal	Any participant that requests to have no further involvement in the study will be marked as withdrawn on the study database.	Any data collected prior to participant withdrawal will be retained and used in the analysis as described in the PIS.

If site staff are made aware of a participant's discontinuation from any study activities, the PI or delegate should record this in the eCRF as soon as possible to ensure the correct procedures are followed by the coordinating centre and the site team. Participants will be asked their reason(s) for withdrawal but are not obliged to provide these.

Withdrawn participants will not be replaced. Data collected prior to withdrawal will be retained and used in the analysis as described in the PIS.

3.4.5 Informed consent

Consent Forms in IDEAL-BACKPACS	Method (e-consent or face-to-face)	Person taking consent (PI, RN, PI or delegate, etc)	Use of legal representatives (Y/N)
Main Study	e-consent	PI, RN or delegate	N

Page 23 of 53 IDEAL BACKPACS Protocol Final Version 1.1 date 09-Oct-l2024

Optional Consents (approval)	completed under sepa	arate study with separ	ate ethical and HRA
Biomarkers (blood) and diagnosis data sharing	face-to-face	PI, RN or delegate	N

Informed e-consent for each participant must be obtained and documented (using the online electronic informed consent form) prior to performing any study related procedure / PROM collection.

It remains the responsibility of the Principal Investigator (or appropriately trained delegate) to ensure informed e-consent is obtained appropriately. An electronic (or paper) Participant Information Sheet (ePIS) will be provided to facilitate this process.

Documentation of consent

After the initial general practice consultation, ideally within 2-3 weeks, potential participants, who have accepted the invite to the study, will receive a telephone, or video, call from a member of the local secondary care research team. The local research team will determine whether the potential participant wishes to enter the study and seek informed e-consent having re-checked eligibility criteria (and suspected red flags) and arrange assessment at the secondary care centre.

The potential participant will be given the opportunity to ask questions throughout the process and sufficient time to consider participating or not. Investigators or delegate(s) will ensure that they adequately explain the aim, anticipated benefits, and potential hazards of taking part in the study to the participant. They will stress that participation is voluntary and so the potential participant is free to decline participation and may withdraw from the study at any time.

If the potential participant expresses an interest in participating in the study, they will be asked to provide written consent using the latest version of the online electronic Informed Consent Form (eICF). Participants will be asked to complete the eICF and write their full name before submitting the online form; the date will be system-generated. The name of the investigator or delegate who provided the study information and the date the eICF was generated will also be recorded within the online system.

The eICF will be retained within the study database. Printable copies will be generated and retained within the Investigator Site File (ISF) and a copy will be made available electronically to the participant. Once the participant is entered into the study, the participant's unique study identification number will be entered on the Informed Consent Form maintained in the ISF.

Details of the informed consent discussions will be recorded in the participant's medical notes. This will include a statement that identifies that the participant is taking part in a clinical study and the name of the study as a minimum.

Subject to prior consent from the participants, once the participant completes the informed consent form the GP will be notified to let them know the patient has consented to the study and asked to record this in their medical notes.

Page 24 of 53 IDEAL BACKPACS Protocol Final Version 1.1 date 09-Oct-l2024

The eICF will include a full audit trail documenting the date and time of information receipt and provision of written informed consent. It will also be necessary for written consent to be fully documented before the system will permit access to the online baseline data collection system.

Throughout the study the participant will have the opportunity to ask questions about the study. Any new information that may be relevant to the participant's continued participation, for example changes to the protocol or study procedures which impact on participants, will be provided through updates to the ePIS which will be notified to participants through text and/or email. Where new information becomes available which may affect the participant's decision to continue, participants will be given time to consider and if happy to continue will be re-consented. Re-consent will be documented through electronic signatures obtained in an updated version of the eICF. The participant's right to withdraw from the study will remain.

Consenting individuals will be booked to a clinic appointment at their local secondary care research centre and will be sent a link to complete online study questionnaire.

If a potential patient declines or is not responsive to the SMS text message within 14 days of receipt, it will be the patient's responsibility to go back to the GP if their symptoms persist.

Additional consent provisions for collection and use of participant data and biological specimens in ancillary studies

During the clinic appointment participants will have the option to consent and take part in an additional separate study, to determine which serological or genetic factors predispose to the development of axSpA. This additional study has existing ethical and HRA approval as part of the National biobank repository and is not covered in this protocol (approved by North West 5 – Haydock Park Research Ethics Committee, reference 99/8/084). Participation would involve consent to take an additional blood sample to be transferred, stored and processed at the University of Manchester and/or King's College, London for biomarker processing (to be covered by a material and data transfer agreement). Consent will be captured on a paper consent form. Where consent for participation in this additional study is given, axSpA diagnosis data from the IDEAL-BACKPACS study will be shared with the University of Manchester and King's College London. This will be shared in a pseudonymised format, and no patient identifiable information will be shared from the IDEAL-BACKPACS study teams. The consent form and/or the blood sample will be labelled with the IDEAL-BACKPACS study ID to allow linkage between the blood sample and the IDEAL-BACKPACS study data. University of Manchester may separately collect patient identifiable information as covered by their ethics approval. Participants will be asked to consent to this data sharing on the national biobank repository consent form. NCTU will hold a copy of this consent form to provide evidence of consent for data sharing and record consent on the trial REDCap database. If the participant declines to participate in this additional study, their participation in the IDEAL-BACKPACS study would not be affected.

Optional consent (on the main study informed consent form) will be sought for imaging data collected as part of the BACKPACS study, (x-ray and MRI images, in pseudonymised form) and stored in the University College London XNAT database, to effectively be included as part of an imaging biobank. This would be used for future appropriately approved research projects, which may be carried out by researchers other than the current team. If the participant declines this, they will continue their participation in the main IDEAL-BACKPACS study.

Page 25 of 53 IDEAL BACKPACS Protocol Final Version 1.1 date 09-Oct-l2024

4. STUDY REGIMEN

Table 4: Summary of assessments for the study

	-					
				STUDY PERIOD		
Timepoint	Invitation and Screening	Eligibility and Enrolment	Consent and questionnaire	Secondary care assessment	Research MRI appointment	PI assessment and reporting
Initial eligibility screen	×					
Contact details obtained	×					
SMS text invitation	×					
Verbal agreement to participate		×				
Confirm eligibility		×				
Participant enrolment		×				
Written informed consent			×			
PROMS completion			×	**		
Clinical assessment				×		
Blood sample (diagnostic test)				×		
X-Ray				×		
MRI					×	
Outcomes reported						×

^{*}If not completed at previous timepoint, Participant Reported Outcome Measures (PROMs) can be completed as part of secondary care assessment.

Page 26 of 53

IDEAL BACKPACS Protocol Final Version 1.1 date 09-Oct-I2024

4.1 Schedule of assessments

4.1.1 Invitation and screening

Initial eligibility to approach is confirmed by the GPC during the primary care attendance. Patients aged 16-50 years who present with chronic back pain (with onset before 45 years) and do not present with any suspected red flags (as described in section 3.4.2 Eligibility criteria) will be approached. Basic screening information obtained from the consultation will be recorded on the pop-up.

4.1.2 Eligibility and enrolment

If the patient agrees for their contact details (name and telephone number) to be used to send an SMS text message invite the GPC will indicate this on the pop-up in the EHR. An SMS text message will be sent from the GP surgery, with assistance from RDN where appropriate, within approximately 14 days of consultation.

The SMS text message will include a link for the electronic Participant Information Sheet, a summary of the consent clauses, and a link to accept or decline the invitation. Translated versions of the Participant Information Sheet may be available for those who do not have English as their primary reading language, as well as videos for those with limited literacy skills.

A member of the research team at the local secondary care site will telephone, or video call the potential participant to discuss the study in more detail, ensure thorough understanding of the study requirements and confirm eligibility.

4.1.3 Consent and PROMS questionnaires

Informed consent is received from patients using the online eICF. Consenting individuals will be booked for a clinic appointment at their local secondary care research centre clinic and will be sent a REDCap database link to complete an online questionnaire prior to their appointment. Up to 3 reminder emails and / or SMS texts may be sent to participants who have not completed their questionnaire.

The questionnaire will include Patient Reported Outcome Measure (PROM) questionnaires as described in Table 5. The questionnaire will be completed online and take around 25 minutes to complete (on a single occasion). The questionnaire will include demographics, brief questions about inflammatory back pain (IBP) symptoms and clinical features (psoriasis and NSAID response), to allow evaluation of whether patient completed screening might contribute towards being an effective screening strategy.

Table 5 Patient Reported Outcome Measures (PROMs)

Variable	Measure	Score
Spinal Pain	Numerical rating scale	0 (no pain) -10 (worst pain)
Fatigue	Functional Assessment of Chronic Illness Therapy (FACIT)[56]	FACIT
	(and/or) Warwick Axial	WASTEd
	Spondyloarthritis Tiredness and	Fatigue 0-10
	Energy scale (WASTEd) [57]	Energy 0-8

Page 27 of 53
IDEAL BACKPACS Protocol Final Version 1.1 date 09-Oct-2024

Disease activity	Bath Ankylosing Spondylitis Disease Activity Index (BASDAI)	Each question is scored on a scale of 0 -10, 0 indicates none and 10 indicates very severe. For the last question, 0 is 0 hours, 5 is one hour and 10 is two or more hours.
Physical function	Bath Ankylosing Spondylitis Disease Activity Function Index (BASFI) [60]	Each question is scored on a scale of 0-10. 0 indicates easy and 10 indicates impossible.
Fibromyalgia	ACR brief criteria [61]	Widespread pain index (0-19)
Quality of life	Evaluation of ankylosing spondylitis quality of life (EASiQoL)[50]	20 questions across the 4 domains of physical function, disease activity, emotional wellbeing and social participation. Each question is scored 0 (no limitation) to 4 (extreme limitation)
NASS self- referral criteria	Back pain onset before aged 40 Insidious onset (i.e. did you bend over and hurt your back) Duration > 3 months Early morning stiffness > 3 months Improves with movement Does not improve with rest Alternating buttock pain Wakes in second half of the night	Yes/no
Physical activity	International physical activity questionnaire and/or General practice physical activity questionnaire	
Work productivity	Work Productivity and Activity Impairment Questionnaire (WPAI): General Health	Measures absenteeism, presenteeism, work productivity and activity impairment
Depression	PROMIS - Depression – Short Form 4a	Each item on the measure is rated on a 5-point scale from 1 indicating never, to 5 indicating always.
Anxiety	PROMIS - Anxiety – Short Form 4a	Each item on the measure is rated on a 5-point scale from 1 indicating never, to 5 indicating always.

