2.3 Secondary Objectives

- Determine the most clinically effective ('superior') referral strategy by comparative
 analysis of the four pre-existing candidate strategies [the Baraliakos [9], modified
 Braun [45], ASAS [44] and CaFaSpA [15]) and the BACKPACS model. The study
 team anticipate that this will result in either the BACKPACS or Baraliakos strategy
 going forward as the 'pop up' in a separate implementation study, IDEALDIRECTED.
- To compare the acceptability and clinical effectiveness of the BACKPACS and Baraliakos referral strategy.
- Evaluate the NASS patient screening questionnaire to determine whether patient self-assessment prior has the potential to reduce delays in diagnosis.
- Estimate of prevalence of axSpA in UK primary care CBP population.
- Evaluate the individual potential screening variables.
- To assess the cost-effectiveness of different axSpA referral strategies, comparing strategies with current care and a comparison between strategies in a fully incremental analysis, applying the rules of simple and extended dominance.

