3.1.3 Index tests

Index tests are the BACKPACS model (to be developed within this study) in addition to existing referral strategies described in Table 3.

Page 17 of 53 IDEAL BACKPACS Protocol Final Version 1.1 date 09-Oct-l2024

Table 3: Index tests

Index tests	Assessment
The Baraliakos strategy [9]	Assesses 3 clinical variables. If 2 or 3 of these variables are present (or a 'second step' HLA-B27 test is positive) then secondary care referral is suggested:
	 improvement in pain with NSAIDs after 48 hours raised CRP (blood test)
	• early morning stiffness (≥ 30minutes)
	This strategy requires follow up after the initial primary care clinic appointment.
The Modified Braun strategy [45]	Assesses 10 clinical variables and if at least 4 of these 10 variables are present then secondary care referral is suggested:
	 low back pain that started before the age of 35 years waking during the second half of the night because of symptoms buttock pain
	 improvement with movement improvement with non-steroidal anti-inflammatory drugs (NSAIDs)
	 a first-degree relative with spondyloarthritis, current/past arthritis,
	• current/past enthesitis
	current/past psoriasisHLA-B27 genetic test
The 'Assessment of SpondyloArthritis international Society (ASAS) strategy [44]	Patients with chronic backpain (≥ 3 months) with onset before 45 years, should be referred if at least one clinical variable is present:
1	Inflammatory backpain HLA-B27 positive
	 Sacroiliitis on imaging, if available (x-ray or MRI) Peripheral manifestations (arthritis, enthesitis and/or dactylitis)
	 Extra-articular manifestations (psoriasis, inflammatory bowel disease and/or uveitis) Family history for spondyloarthritis
	Good response to NSAIDS Acute elevated phase reactants (c-reactive protein or erythrocyte sedimentation rate)
The CaFaSpA referral strategy[15]	Easy to use and was developed in a primary care setting but was not adopted by NICE spondyloarthritis clinical guideline[3], as the study cohort reported a much lower than expected prevalence of HLA-B27 positive individuals. The explanation for this may be related to the study having a lengthy retrospective recruitment time

Page 18 of 53 IDEAL BACKPACS Protocol Final Version 1.1 date 09-Oct-l2024

for individuals with CBP (median 10 years), whilst
excluding patients diagnosed with axSpA during this
period; many of the excluded individuals with axSpA
would have been HLA-B27 positive. This approach

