3.4. Selection and withdrawal of participants

3.4.1 Recruitment

Study Setting

Patients will be identified from General Practices (GP) acting as Patient Identification centres (PIC) and then clinically assessed at their local secondary care research centre site (all sited in rheumatology services with strong axSpA expertise). GP practices surrounding each research centre will identify patients presenting with CBP by Systemized Nomenclature of Medicine (SNOMED) code or prior identification as a back pain consultation. General Practice Clinicians (GPCs) responsible for evaluating patients with back pain will reflect the present clinical diversity of health professional expertise assessing this patient group and may include general practitioners, physician associates, first contact physiotherapists and practice nurses.

Participant Identification, screening, and recruitment

Participants may be approached by a variety of methods:

1) Pop-up method

Patient with back pain consults their general practice, dependent on the availability of staff at the GP practice, patients may be given a miniaturised copy of the study poster to prompt discussion during their consultation.

GPC enters 'back pain' SNOMED code, triggering patient eligibility screen template (pop-up) in electronic health record (EHR) if patient is aged between 16-50 years.

GPCs will assess for suspected red flag exclusion criteria in potential participants (see 3.4.2 Eligibility criteria). If a patient is potentially eligible and the GPC deems them suitable for the study, they will briefly introduce the study and ask the patient whether they would be willing to receive an SMS invitation to the study. The GPC will complete a simple and brief

Page 20 of 53

IDEAL BACKPACS Protocol Final Version 1.1 date 09-Oct-l2024

electronic pop-up to confirm the patient has current back pain and more than 3 consecutive months of chronic back pain in the last 12 months, absence of red flags and verbal agreement for an SMS invite to be sent. If the patient is not eligible, or not interested in being contacted about the study, the GPC will indicate this within the pop-up. If a potential participant fails screening, and then later presents with > 3 months back pain, they can be re-screened for eligibility at the GP primary care assessment stage.

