3.4.2 Eligibility criteria

Inclusion criteria

- Aged 16-50 years with onset of chronic back (cervical/thoracic/lumbar) pain before 45 years.
- Current back pain and at least 3 consecutive months of chronic back pain in the last 12 months.
- Ability to provide written/electronic informed consent.
- Willingness and ability to undergo all study assessments (i.e. clinical examination, X-ray, MRI, blood sample collection).

Exclusion criteria

- Existing diagnosis of axSpA.
- Existing diagnosis of inflammatory arthritis.
- GPC deems unsuitable.
- Radiation of leg pain below the knee (i.e. neuralgia/sciatica)
- Contraindications to MRI, e.g.:
 - o Pacemaker
 - Other ferrous metal in situ
 - Pregnancy (0-12 months post-partum)
 - Claustrophobia

Suspected red flags in the history or clinical examination that may indicate further investigation or referral for possible serious underlying pathology:

- Cauda Equina Syndrome
- Spinal Fracture
- Cancer
- Bone/disc infection

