5. STATISTICS

5.1 Methods

The analysis and reporting of the study will be in accordance with STAndards for Reporting of Diagnostic Accuracy (STARD) and Transparent Reporting of a multivariable prediction model for Individual Prognosis Or Diagnosis + Artificial Intelligence (TRIPOD+AI) reporting guidelines. A full statistical analysis plan (SAP) will be developed and agreed prior to database lock.

Descriptive statistics will be used to describe baseline characteristics, prevalence of axSpA symptom duration, pain severity and other clinical factors.

For each of the index tests (described in section 3.3) sensitivity, specificity, positive and negative predictive values, and likelihood ratios (and associated 95% confidence intervals) will be calculated to assess diagnostic accuracy and clinical utility, along with the area under the (receiver-operator characteristic) curve and calibration. Estimates of comparative accuracy between models will be obtained using appropriate statistical models and reported with 95% confidence intervals. Where necessary we will recalibrate models to allow for a difference in prevalence of disease in our population.

To develop the BACKPACS strategy we will pre-specify 12 key variables to include in the initial modelling, although we would seek to develop models with 3 or 4 variables which would be most suitable for clinical use. Internal validation using 200 bootstrap samples and shrinkage will correct for overfitting. A prediction model equation or simplified clinical score will be presented in a user-friendly format, with performance summarised using discrimination (c-index) and calibration (plot in quartile risk groups) outcomes and graphs. Based on estimates of sensitivity and specificity, we will determine a sensible cut-off value above which patients could be referred to a rheumatologist.

Analyses will be conducted in Stata 18.0 or later.

Planned Subgroup Analyses

Where feasible, subgroup analyses will be employed to assess whether there are differences in accuracy of the referral strategies for the following groups:

Page 35 of 53 IDEAL BACKPACS Protocol Final Version 1.1 date 09-Oct-2024

- Age of symptomatic onset before 35 years vs. onset after 35 years
- Males/Females
- Caucasian vs non-Caucasian (related to variations in disease incidence with race)

Subgroup analyses will be conducted by including an appropriate interaction term in the statistical model.

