86. Braun V, Clarke V: Using thematic analysis in psychology. Qualitative Research in Psychology

2006, 3(2):77-101.

- 87. Braun VC, V.: Thematic analysis. Research methods in social sciences: An A-Z of key concepts: Open University Press.; 2021.
- 88. Creswell JW, Miller DL: Determining Validity in Qualitative Inquiry. Theory Into Practice 2000, 39(3):124-130.

Appendices

Appendix 1: Specification of the variables used for the ASAS-Criteria for classification of Axial Spondylarthritis

Clinical Feature of axSpA	Definition
Inflammatory back pain (IBP)	IBP according to experts: 4 out of 5 of the
, , , , , , , , , , , , , , , , , , ,	following parameters present:
	1. Age at onset < 40 years
	2. Insidious onset
	3. Improvement with exercise
	4. No improvement with rest
	5. Pain at night (with improvement upon getting up)
Good response to NSAIDs	24-48 hours after a full dose of a non-steroidal
	anti-inflammatory drug (NSAID) the back pain is
	not present any more or much better.
	(the clinical co-applicants on the PGfAR IDEAL
	grant have concluded that response after one
	week would be more appropriate)
Arthritis	Past or present active synovitis diagnosed by a physician.
Dactylitis	Past or present dactylitis diagnosed by a
	physician.
Enthesitis	Heel enthesitis: past or present spontaneous
	pain or tenderness at examination of the site of
	the insertion of the Achilles tendon or plantar
	fascia at the calcaneus.
	(a broader evaluation of enthesitis is also being
	evaluated for the IDEAL study cohort)
Psoriasis	Past or present psoriasis diagnosed by a
	clinician.
Inflammatory bowel disease (IBD)	Past or present Crohn's disease or ulcerative
	colitis diagnosed by a physician.
Uveitis anterior	Past or present uveitis anterior, confirmed by an
	ophthalmologist.
Family history	Presence in first-degree or second-degree
	relatives of any of the following:
	a. Ankylosing spondylitis
	b. Psoriasis
	c. Uveitis
	d. Reactive arthritis
	e. IBD
HLA-B27	Positive testing according to standard laboratory
	techniques.
Elevated CRP	C-reactive protein above upper normal limit in
	the presence of back pain, after exclusion of
	other causes for elevated CRP concentration.

Page 53 of 53 IDEAL BACKPACS Protocol Final Version 1.1 date 09-Oct-2024

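### The NASS insidious-onset item is explained by its opposite, its stiffness item carries a doubtful unit, and the protocol commits no accuracy analysis to NASS although evaluating it is a secondary objective

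*Protocol*

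**What the plan says.** Table 5 of the protocol (section 4.1.3) lists eight NASS self-referral criteria. The first is "Back pain onset before aged 40". The next three run "Insidious onset (i.e. did you bend over and hurt your back) Duration > 3 months Early morning stiffness > 3 months". The score column says only that the answers are yes or no. No direction, total or cut-off is given. Participants complete the questionnaire themselves, once, and section 8.3.2 says that no data queries will be raised on participant-completed questionnaires.

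The same features appear elsewhere:

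- **Onset:** Appendix 1 counts "2. Insidious onset" as one of five parameters of inflammatory back pain.
- **Stiffness:** Table 3 gives the Baraliakos stiffness variable as at least 30 minutes.
- **Duration:** section 3.4.2 requires "Current back pain and at least 3 consecutive months of chronic back pain in the last 12 months", and under section 3.4.1 the GP pop-up is there to "confirm the patient has current back pain and more than 3 consecutive months of chronic back pain in the last 12 months".

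On the analysis, section 2.3 lists the objective "Evaluate the NASS patient screening questionnaire to determine whether patient self-assessment prior has the potential to reduce delays in diagnosis". Section 3.1.3 states "Index tests are the BACKPACS model (to be developed within this study) in addition to existing referral strategies described in Table 3". Table 3 contains Baraliakos, modified Braun, ASAS and CaFaSpA, but not NASS. Section 5.1 then promises accuracy measures "For each of the index tests (described in section 3.3) sensitivity, specificity, positive and negative predictive values, and likelihood ratios".

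**The concern.** The onset item has a label and an explanation that point in opposite directions. Someone who answers the explanation literally is recorded as positive for insidious onset when the onset was sudden, and as negative when it was gradual. Someone who answers the label is recorded correctly. The protocol does not say which of the two the participant sees, or how a yes is scored.

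The stiffness item carries the same three-month cut as the duration item just before it. Read literally, it asks how long the complaint has existed, not how long stiffness lasts in the morning.

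The protocol also names an evaluation of NASS as an objective, then defines its index tests without NASS and ties its accuracy measures to index tests. A reader cannot tell from the protocol that sensitivity, specificity or likelihood ratios will be reported for NASS.

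What is at stake is a secondary objective. Section 1.2 says that the NASS self-screening tool would benefit from an evidence base, and this study would supply it. A reversed or mixed item would make the tool look worse than it is. With one completion and no queries, the answers are hard to repair afterwards.

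**Working it through.** The protocol states no figure for NASS, so there is none to reproduce. The first three steps set the texts side by side. The last two are illustrations on assumed values.

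**1. Onset.** Label: insidious. Explanation: a bending injury. Appendix 1: insidious onset counts towards inflammatory back pain. A yes to the explanation therefore contradicts both the label and Appendix 1.

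**2. Stiffness and duration.** Table 5 has stiffness in months; Table 3 has it in minutes, for a different tool. The duration item repeats the entry requirement, so in practice every participant meets it. The one exception is a participant with exactly three months, who is eligible under 3.4.2 but fails a strict more-than-three item. An item that everyone meets has sensitivity about 1 and specificity about 0, so its likelihood ratio is about 1. It adds one point to every count and shifts any cut-off by one.

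**3. Analysis.** Objective (2.3): NASS included. Index tests (3.1.3 and Table 3): NASS absent. Accuracy measures (5.1): index tests only. Section 5.1 also points to section 3.3 for the index tests, which are in 3.1.3.

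**4. Size if the onset item is fully reversed.** As intended, LR+ = Se/(1 − Sp). Reversed, sensitivity becomes 1 − Se and specificity 1 − Sp, so LR+ = (1 − Se)/Sp. The count score is assumed to be eight items: seven informative ones with equal Se and Sp, independent given disease status, plus the duration item always yes. AUC is computed exactly from the distribution of the count.

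| Assumed Se / Sp | LR+ intended | LR+ reversed | AUC intended | AUC reversed |
|---|---|---|---|---|
| 0.6 / 0.6 | 0.6/0.4 = 1.50 | 0.4/0.6 = 0.67 | 0.771 | 0.703 |
| 0.7 / 0.6 | 0.7/0.4 = 1.75 | 0.3/0.6 = 0.50 | 0.872 | 0.794 |
| 0.7 / 0.7 | 0.7/0.3 = 2.33 | 0.3/0.7 = 0.43 | 0.938 | 0.868 |
| 0.8 / 0.5 | 0.8/0.5 = 1.60 | 0.2/0.5 = 0.40 | 0.883 | 0.804 |

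The AUC losses are 0.068, 0.078, 0.070 and 0.079. Removing the duration item leaves AUC unchanged (0.771 with or without it in the first row).

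A second illustration uses unequal assumed frequencies (cases/non-cases): onset before 40, 93/80%; insidious 75/50%; duration 100/100%; stiffness, movement and rest 70/50% each; buttock pain 35/20%; night waking 60/40%. AUC falls from 0.77 to 0.68. At an assumed cut of five or more, sensitivity falls from 86% to 74% while specificity stays at 53%.

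**5. Size if the answers are mixed.** Suppose a fraction m answers the explanation and the rest the label, regardless of disease status. The item's sensitivity is then (1 − m)Se + m(1 − Se), and its specificity (1 − m)Sp + m(1 − Sp). At m = 0.5 both equal 0.5, whatever Se and Sp are, so LR+ = 0.5/0.5 = 1.00 and the item carries no information. Reversing the code for everyone leaves it at 1.00. At m = 1, reversing the code restores the intended values exactly. Consistent reversal can therefore be repaired; mixed answers cannot.

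**The case against.** The strongest objection is that Table 5 summarises the measures and does not reproduce the form. Its entries are shorthand criteria, and neither the REDCap wording nor the coding is shown. This stands. A reader might infer that the objective will get a wrong answer, but the documents support only that it would if the form follows Table 5 and nobody recodes.

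A reader might also infer that the objective gets no answer at all. That goes too far. The items are collected, section 4.1.3 says that patient-completed questions are there to evaluate patient screening, a further objective covers the individual screening variables, and the SAP may define the NASS analysis. What remains is that the protocol itself fixes a list of index tests which omits a tool its objectives name.

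It may be tempting to call the duration item faulty. It is not. NASS is an existing tool for general users, and the item is constant here through eligibility. It is uninformative in this cohort and does not bias AUC.

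On stiffness, the 30-minute cut belongs to Baraliakos, and the original NASS wording is not in the documents. Imposing minutes could alter the tool under evaluation. Length of stiffness is also captured by the last BASDAI question in Table 5. So the unit is a point to check, not a proven error.

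Finally, one might read the objective as a claim to measure diagnostic delay, which a single questionnaire completed after consent could not support. The objective speaks only of potential to reduce delays, so that criticism does not hold.

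**Conclusion.** The point holds in a limited form. The onset item in Table 5 contradicts its own label and Appendix 1, and no scoring direction resolves it. The stiffness unit does not match the only stiffness definition in Table 3 and needs checking against the original tool. NASS is a stated object of evaluation for which sections 3.1.3 and 5.1 commit no accuracy measures.

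The AUC loss of about 0.07–0.08 (0.09 in the second illustration) and the fall in the item's likelihood ratio are not properties of this plan. They assume a simple sum score, item accuracies or frequencies that the protocol does not give, independence between items, complete reversal and no recoding. Independence is doubtful for the stiffness, movement and rest items.

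The matter should be corrected because it affects a secondary objective, costs little, and becomes harder to repair as answers accumulate. It does not touch either co-primary objective.

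**What to change.** 1. Check the REDCap form against the original NASS questionnaire before changing anything.
2. Word the onset item in one direction, with yes meaning insidious: for instance, ask whether the pain came on gradually, without an injury or sudden movement. State the scoring direction in Table 5.
3. Reconcile the stiffness item with the original tool, and correct the unit only if Table 5 departs from it.
4. Add NASS to section 3.1.3, or extend section 5.1 so that its accuracy is reported against the primary reference standard. Correct the cross-reference in 5.1 from 3.3 to 3.1.3 at the same time.
5. Note that the duration item is met through eligibility and is therefore uninformative in this cohort.
6. Act on onset answers already collected only if the live form carried the faulty wording. Recode them if they were consistently reversed. Set them aside if label and explanation were shown together. If the live form was worded correctly, leave the data alone and correct Table 5 only.

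The cost is a small amendment to the protocol and possibly the form, plus one more row in the accuracy table. The downside is that some onset answers, and possibly some stiffness answers, from participants already entered may be lost.
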